15 VULNERABLE POPULATION

This clinical investigation will not be conducted in children, or in any other vulnerable populations.

If the patient is not capable of giving consent, the written consent of the patient's legal representative will be required before participation in the investigation (see Section 13, page 70).

16 SUSPENSION OR PREMATURE TERMINATION OF THE CLINICAL INVESTIGATION

The Sponsor may suspend or prematurely terminate the clinical investigation for any safety, ethical or administrative reason at any time. The Investigator, IEC or Competent Authority may suspend or prematurely terminate participation at the investigational sites for which they are responsible.

If the investigation is prematurely terminated or suspended, the Sponsor should promptly inform the Investigators/institutions, the IEC and the Competent Authority of the termination or suspension with the reason(s) for the termination or suspension, as per the applicable regulatory requirement(s).

If the suspension or premature termination is in the interest of safety, the Sponsor shall inform all other principal Investigators.

17 PUBLICATION POLICY

The data resulting from this investigation will be the proprietary information of Sponsor. None of the data resulting from this investigation will be allowed to be presented or published in any form, by the Investigator or any other person, without the prior approval of Sponsor.

At the end of the investigation, a clinical investigation report will be written by the Sponsor. The draft reports will be discussed with the coordinating Investigator and with the Sponsor.

19 APPENDICES

19.1 Appendix I: T2259 Leaflet

LEAFLET:

Read the instruction manual

THEALOZ DUO FORTE

Enhance protection, hydration and lubrication of the eye for treatment of moderate to severe dry eye syndrome associated with superficial keratitis.

ABAK Bottle - Preservative free.

COMPOSITION:

Trehalose 6.00 g

Sodium hyaluronate 0.20 g

Sodium Chloride, Trometamol, Hydrochloric acid, Water for injections....to 100 ml

NAME AND ADDRESS OF MANUFACTURER:

Laboratoires THEA – [name] - [name]

WHEN TO USE THEALOZ DUO FORTE:

THEALOZ DUO FORTE contains a solution for administration into the conjunctival cul-de-sac of the eye and can be used with contact lenses. THEALOZ DUO FORTE can be used when you have discomfort, stinging, irritated, red, watery eyes, that are sensitive to bright light, bloodshot or when you have the foreign body sensation. These symptoms can be caused by external factors such as wind, smoke, pollution, dust, sunny or cold conditions, dry heat, air conditioning, plane journeys, and prolonged use of visual display terminal.

THEALOZ DUO FORTE is preservative-free which helps provide good levels of tolerance on the eye. The solution can be used by contact lens wearers who wear any type of contact lens and it provides immediate comfort that lasts all day long.

PROPERTIES:

THEALOZ DUO FORTE is a sterile, preservative free, isotonic and pH neutral aqueous ophthalmic solution. Its main ingredients are trehalose, a disaccharide present in many plants

and animals, and sodium hyaluronate, a polysaccharide naturally present in the eye.

Trehalose protects and hydrates. For these reasons, it is essential in the anhydrobiotic process used in certain tiny organisms (a slow metabolism that helps them live in dry conditions). Trehalose protects and stabilises membranes and proteins of the cells exposed to damaging conditions like in the absence of water.

Sodium hyaluronate is natural polysaccharide found in the human eye with proven benefits to hydrate and lubricate the surface of the eye. It keeps the solution on the eye's surface giving long lasting relief and cutting down the healing time of the corneal epithelium (the clear surface on the eye).

The innovative combination of Trehalose and Sodium hyaluronate in THEALOZ DUO FORTE protects, hydrates and lubricates the eye surface for a long time and with a maximum comfort.

THEALOZ DUO FORTE is supplied in the ABAK multi-dose bottle to avoid the use of chemical preservatives. This innovative and patented device provides eye drops through a 0.2 µm filter, preventing any bacterial contamination of the solution. The solution is protected and can be used for up to 2 months after the bottle is opened.

SPECIAL WARNINGS AND SPECIAL PRECAUTIONS FOR USE:

- Do not use if you are allergic to any of the ingredients.
- Do not touch the surface of the eye with the tip of the bottle.
- Do not inject, do not swallow.
- If the safety ring is damaged, do not use the product.

KEEP OUT OF THE SIGHT AND REACH OF CHILDREN.

INTERACTIONS:

Wait at least 10 minutes between using two different eye products

HOW TO USE THIS PRODUCT:

METHOD AND ROUTE OF ADMINISTRATION:

USE ONLY IN THE EYE.

- Wash hands well before use,
- Do not touch the eyes or eyelids with the tip of the bottle, especially when you think you may have an eye infection,
- Drop one drop in the lower conjunctival sac (the space between the eye and eyelid), while gently pulling the lower lid downwards and looking up.
- Put the cap back after use.

DOSAGE:

1 drop in each eye, 2 to 4 times daily.

[figure not shown]
THEALOZ DUO FORTE can be used when wearing contact lenses.

**SIDE EFFECTS:**

You may have mild eye irritation and ocular hyperaemia, although this is very unusual.

STORAGE OF THE PRODUCT:

Do not keep an open bottle for more than 2 months.

[figure not shown]
Store below 25°C

DO NOT USE AFTER THE EXPIRY DATE CLEARLY MARKED ON THE OUTER CARTON. The expiry date refers to the product in intact packaging, stored correctly. Do not use the bottle if it is damaged.

INSTRUCTIONS UPDATED: 10/2018.

Manufacturer

Store below 25°C

Do not use if package is damaged

Sterilised using aseptic processing techniques

Consult instructions for use

Caution

Use-by date

Batch number

19.2 Appendix II: Vismed® Multi leaflet

LUBRICANT EYE DROPS

Instruction leaflet

VISMED® MULTI
0.18% sodium hyaluronate obtained through fermentation.

Lubricant eye drops.

Sterile, preservative-free.

Composition:

1 ml of solution contains 1.8 mg sodium hyaluronate, sodium chloride, potassium chloride, disodium phosphate, sodium citrate, magnesium chloride, calcium chloride and purified water. The solution is hypotonic.

Indications:

Moderate and severe sensations of ocular dryness.

Contraindications:

Hypersensitivity to one of the ingredients of the product.

Interactions:

Do not administer VISMED® MULTI at the same time as other eye medication or products as it could change the effects.

Side effects:

In rare cases, temporary effects, such as irritation of the conjunctiva, sensation of something in the eye, redness or a burning sensation, as well as momentary blurred vision can occur.

Dosage and method of administration:

Remove the security band before first use. Take off the protective cap. Tilt your head backwards and position the tip of the bottle above the eye to be treated. Pull the bottom eyelid downwards with your index finger. Squeeze the body of the bottle and one drop of VISMED® MULTI will be released easily (see illustrations). Unless recommended otherwise, place 1 to

2 drops of VISMED® MULTI into the eye as often as needed. Blinking several times will ensure a transparent and durable film of the solution is spread evenly across the surface of the eye. VISMED® MULTI can be used while wearing contact lenses (soft and hard).

Precautions:

To not touch the tip of the bottle and do not touch the surface of the eye with the tip of the bottle. Replace the protective cap on the VISMED® MULTI bottle after use. Do not use VISMED® MULTI if the bottle is damaged. After the first use, VISMED® MULTI can be used for up to 6 months. After opening, dispose of any unused solution after 6 months. After this time, sterility cannot be assured and this may be associated with a risk of infection.

Store below 30°C. Do not freeze. Do not use VISMED® MULTI after the expiry date mentioned on the bottle and box. If your condition persists while using VISMED® MULTI, see a doctor. Keep out of the reach of children.

Properties and mechanism of action:

VISMED® MULTI contains sodium hyaluronate, a natural polymer that is also present in the structures of the human eye. The specific physical characteristics of sodium hyaluronate give VISMED® MULTI its viscoelastic and water retaining properties. Therefore, VISMED® MULTI forms a stable film on the surface of the eye, which is very slowly dispersed through blinking. VISMED® MULTI combines a long-lasting effect with maximum comfort. Due to its specific composition, VISMED® MULTI is very well tolerated. VISMED® MULTI does not contain any preservatives.

Presentation: 15 ml of solution in a multi-dose bottle. Last revision: 2018-01

Instructions for use on the back.

Distributor:

Horus Pharma – [name]
[name]
[contact], www.horus-pharma.fr
15 ml – ACL Code: 3664490000031

TRB CHEMEDICA AG
[name]
[name]

[figure not shown]

VISMED® MULTI

1

[figure not shown]

2

LOT

3

4

STERILE A

120156/1
S01.18
CAVMT017-07/17
NOT24908V02

The Statistical analysis Plan (SAP) aims to describe the statistical analyses that will be performed for the study **LT2259-001**, based on the study protocol (Version 3.0 – 3 January 2020) and the e-Case Report Form (e-CRF) (Version MSC003, dated on 06 APR 2020), in accordance with ICH Guidelines and the general statistical principles.

This document is written by the AXONAL-BIOSTATEM statistician and reviewed and approved by the Sponsor of the Investigation (Laboratoires Théa) before the database lock.

1 STUDY OBJECTIVES

1.1 Primary objective

The primary objective of this study is to demonstrate the non-inferiority of T2259 versus Vismed® Multi in terms of performance.

Non-inferiority will be tested by calculating the bilateral 95% CI of the difference between groups (T2259 – Vismed® Multi) of the change from baseline of total ocular staining according to Oxford 0-15 grading scheme on Day 35. If the upper bound is no higher than 2 points, it will be concluded that the null hypothesis can be rejected and that the performance of T2259 is non-inferior to that of Vismed® Multi.

The non-inferiority analysis will be provided primarily in the PP population and confirmed in the FAS population.

1.2 Secondary objective

The secondary objective of the investigation is to evaluate the safety and the performance of T2259 versus Vismed® Multi.

2 STUDY DESIGN

2.1 Overview

This is a multicentre, randomised study, investigator-masked, 2 parallel groups (T2259 versus Vismed® Multi) of 38 evaluable patients each.

The patients were randomised after a run-in-period of 7 to 10 days with preservative free artificial tears (Hydrabak®, one drop in each eye 3 to 6 times daily). Then, they were treated with either T2259 or the reference product (Vismed® Multi) for 84 days (\pm 7 days).

Investigation visits were performed as following:

Day 1-10/Day 1-7	Selection visit (Visit 1)
Day 1	Randomisation/ Inclusion visit (Visit 2)
Day 8 (\pm 1)	Visit 3 Optional Visit (if the investigator and/or the patient thinks it is necessary)
Day 35 (\pm 3)	Visit 4
Day 84 (\pm 7)	Final visit (Visit 5)

The Visits V2, V3, V4 and V5 should have been performed at the same hour (± 4 hours).

Reclassification of visits:

All “premature withdrawal” visits will be reclassified as decided in BR Meeting. Number of days between premature withdrawal visits and randomisation visit will be calculated and depending of this number of days, visits will be reclassified to the nearest planned non-missing visit.

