Visit #2 will take place 7 to 10 days after the selection visit (visit #1) and will consist of the following procedures and examinations (to be done according to the following order and in **each eye** for ocular assessments).

By **the first investigator** in charge of all examinations and safety assessment during the investigation:

- Questioning about Hydrabak® compliance during the run-in period;
- Questioning about concomitant ocular and non-ocular treatments;
- Questioning about AEs during the run-in period;
- Measurement of OSDI score;
- Questioning about ocular symptoms;
- Measurement of conjunctival hyperaemia with McMonnies photographic scale;
- Slit lamp examination for measuring:
 - TBUT,
 - Oxford 0-15 grading scheme (corneal staining by fluorescein, temporal and nasal staining by lissamine),
 - Van Bijsterveld score (lissamine green staining) / optional examination;
- Schirmer test (without anaesthesia);
- Adverse events;
- Verification of inclusion/exclusion criteria;
- Randomisation.

At investigation sites equipped with Optical Quality Analysing System (OQAS):

- Evaluation of OSI using double pass aberrometry.

For patients with severe Dry Eye, defined as OSDI \geq 33 and/or Corneal Fluorescein Staining \geq 3

- Impression cytology (for HLA-DR).

By **the second investigator** responsible for dispensation:

- Explanations of dosing regimen for IMD;
- IMD dispensation for the period Day 1 to Day 35 according to allocated treatment number.

6.4.3 **Visit #3: Day 8 ± 1 day (optional visit)**

Visit #3 will take place 6 to 8 days after the randomisation visit (visit #2) and can be performed if investigator and/or patient thinks it is necessary.

This visit will consist of the following procedures and examinations (to be done according to the following order and in **each eye** for ocular assessments).

By **the first investigator** in charge of all examinations and safety assessment during the investigation:

- Questioning about concomitant ocular and non-ocular treatment;
- Questioning about AEs between Day 1 and Day 8;
- Measurement of OSDI score;
- Questioning about ocular symptoms;
- Measurement of conjunctival hyperaemia with McMonnies photographic scale;
- Slit lamp examination:
 - TBUT,
 - Oxford 0-15 grading scheme (corneal coloration by fluorescein, temporal and nasal staining by lissamine),
 - Van Bijsterveld score (lissamine green staining) / optional examination;
- Schirmer test (without anaesthesia).

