5.3 Multiple Imputations for Handling of Dropouts or Missing data

Treatment Emergent Adverse Events (TEAEs) are AEs that occurred after the first IMD instillation. AEs that occurred the day of the first IMD instillation will be reviewed in detail to identify if AEs appeared before or after the first treatment with IMD (to decide if they have to be considered as TEAEs or not). If no additional information is available, they will be treated as TEAEs.

By default, AEs will be considered as TEAEs if no enough information is available.

For primary analysis performed on FAS, Last Observation Carried Forward (LOCF) method will be applied in case of missing value.

In order to define the type of treatments (previous, concomitant or post-study) and treatment duration, partially start/end dates will be imputed with the following rules for calculations:

For treatment start date:

- If only the day is missing, it will be considered as 1st for calculations
- If only the year is completed, day and month will be considered as January 1st for calculations

For treatment end date:

- If only the day is missing, it will be considered as the last day of the month for calculations
- If only the year is completed, day and month will be considered as December 31st for calculations

If the date is totally missing, it will not be replaced.

Other missing data will not be replaced.

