6.7.2 Secondary Performance Endpoints

Secondary performance endpoints analysis will be provided in the PP population and the FAS population and for both worse eye and contralateral eye.

- Oxford total score

Descriptive summaries for the Oxford Total score, change from baseline and summaries by panel will be repeated for the contralateral eye in the same manner as for the Primary Endpoint analysis.

Change from baseline in Oxford total score at D8 and D84 on worst eye and at D8, D35 and D84 in contralateral eye will be analysed using an ANCOVA model, constructed using main effects of investigation product and baseline score as covariate. The LS ("adjusted") means for each treatment arm and estimates of the difference between groups (T2259 – Vismed® Multi) will be presented along with the respective two-sided, 95% CI. Two-sided p-values will be presented for the treatment difference.

- Van Bijsterveld score* (lissamine green staining)

All items used to calculate the total score will be tabulated, by treatment group, with frequency and percentage at each time point (Selection visit, D1, D8, D35 and D84). Total score and change from baseline will be tabulated, by treatment group, with all parameters specified in part 7.3 (quantitative variables). These analyses will be performed at Day 8, Day 35 and Day 84 on both worst and contralateral eye.

Change from baseline in Van Bijsterveld total score at D8, D35 and D84 for both worst and contralateral eye will be analysed using an ANCOVA model, constructed using main effects of investigation product and baseline score as covariate. The LS ("adjusted") means for each treatment arm and estimates of the difference between groups (T2259 – Vismed® Multi) will be presented along with the respective two-sided, 95% CI. Two-sided p-values will be presented for the treatment difference.

*Assessment recorded for each eye will be analysed for the worst eye and the contralateral eye.

- DEQ-5 total score

Each question (1a, 1b, 2a, 2b and 3) will be presented, by treatment group, by frequency and percentage at each time point (Selection visit, D35 and D84). Total score and change from baseline will be tabulated, by treatment group. These analyses will be performed at Day 35 and Day 84.

Change from baseline in DEQ-5 total score at D35 and D84 will be analysed using an ANCOVA model, constructed using main effects of investigation product and baseline score as

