covariate. The LS ("adjusted") means for each treatment arm and estimates of the difference between groups (T2259 – Vismed® Multi) will be presented along with the respective two-sided, 95% CI. Two-sided p-values will be presented for the treatment difference.

- OSDI (Ocular Surface Disease Index) total score

Each question (from Q1 to Q12) will be presented, by treatment group, by frequency and percentage at each time point (D1, D8, D35 and D84). Total score and change from baseline will be tabulated, by treatment group. These analyses will be performed at Day 8, Day 35 and Day 84.

Change from baseline in OSDI total score will be analysed at D8, D35 and D84 using an ANCOVA model, constructed using main effects of investigation product and baseline score as covariate. The LS ("adjusted") means for each treatment arm and estimates of the difference between groups (T2259 – Vismed® Multi) will be presented along with the respective two-sided, 95% CI. Two-sided p-values will be presented for the treatment difference.

Moreover, at each time point, OSDI total score will be presented, by treatment group, by frequency and percentage with the following modalities: Normal ([0-13[]), Mild ([13-23[]), Moderate ([23-33[]) and Severe ([33-100]) and Cochran-Mantel-Haenszel (CMH) test will be performed for D35 and D84.

- Schirmer Test result* (without anaesthesia)

Schirmer test results at each time point (D1, D8, D35 and D84) and change from baseline will be tabulated, by treatment group. These analyses will be performed at Day 1, Day 8, Day 35 and Day 84 on both worst and contralateral eye.

Change from baseline in Schirmer Test result will be analysed at D8, D35 and D84 on both worst and contralateral eye using an ANCOVA model, constructed using main effects of investigation product and baseline score as covariate. The LS ("adjusted") means for each treatment arm and estimates of the difference between groups (T2259 – Vismed® Multi) will be presented along with the respective two-sided, 95% CI. Two-sided p-values will be presented for the treatment difference.

*Assessment recorded for each eye will be analysed for the worst eye and the contralateral eye.

- TBUT* (Tear Break-Up Time)

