Each measure of TBUT will be presented, by treatment group, by frequency and percentage at each time point. Mean TBUT at each time point (D1, D8, D35 and D84) and change from baseline will be tabulated, by treatment group for both worst and contralateral eye. These analyses will be performed at Day 8, Day 35 and Day 84.

Change from baseline in mean TBUT will be analysed at D8, D35 and D84 on both worst and contralateral eye using an ANCOVA model, constructed using main effects of investigation product and baseline score as covariate. The LS ("adjusted") means for each treatment arm and estimates of the difference between groups (T2259 – Vismed® Multi) will be presented along with the respective two-sided, 95% CI. Two-sided p-values will be presented for the treatment difference.

- Conjunctival hyperaemia* using McMonnies photographic scale

Score of Conjunctival hyperaemia will be tabulated, by treatment group, at each time point

(D1, D8, D35 and D84) using frequency and percentage. Treatment groups will be compared using a Cochran-Mantel-Haenszel (CMH) test based on modified ridit scores (using SCORES=MODRIDIT option in FREQ procedure), stratified by the baseline value.

*Assessment recorded for each eye will be analysed for the worst eye and the contralateral eye.

- Dry eye symptoms

Each Dry Eye symptom at Day 8, Day 35 and Day 84 will be compared between treatment group using percentage of patient with an improvement, a stability or a degradation from baseline using a Cochran-Mantel-Haenszel (CMH) test.

Total score and change from baseline will be tabulated, by treatment group. These analyses will be performed at Day 8, Day 35 and Day 84.

Change from baseline in Dry Eye Symptoms total score will be analysed at D8, D35 and D84 using an ANCOVA model, constructed using main effects of investigation product and baseline score as covariate. The LS ("adjusted") means for each treatment arm and estimates of the difference between groups (T2259 – Vismed® Multi) will be presented along with the respective two-sided, 95% CI. Two-sided p-values will be presented for the treatment difference.

- Performance assessment

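### Formal between-group tests are planned at the optional Day 8 visit, where attendance is decided after randomisation and the comparison is open to selection bias

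*SAP*

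**What the plan says.** **Status of the visit.** SAP 2.1 lists Day 8 as "Visit 3 Optional Visit (if the investigator and/or the patient thinks it is necessary". Protocol 6.4.3 says that the visit "can be performed if investigator and/or patient thinks it is necessary". Footnote 6 to the visit schedule repeats this in both documents. No clinical trigger, expected attendance or rule for holding the visit is given.

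**Planned tests.** SAP 6.7.2 analyses "Change from baseline in Oxford total score at D8 and D84 on worst eye and at D8, D35 and D84 in contralateral eye" by ANCOVA and states that "Two-sided p-values will be presented for the treatment difference". The same form recurs for the other continuous endpoints, for example "Change from baseline in OSDI total score will be analysed at D8, D35 and D84 using an ANCOVA model" and "Change from baseline in mean TBUT will be analysed at D8, D35 and D84 on both worst and contralateral eye using an ANCOVA model". For symptoms, "Each Dry Eye symptom at Day 8, Day 35 and Day 84 will be compared between treatment group" by a CMH test. Conjunctival hyperaemia is tabulated at Day 8 and compared by CMH; Protocol 7.3.3 names Day 8 for that comparison. All of this is done in both PP and FAS.

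**Missing values.** SAP 5.3 applies LOCF to the primary analysis on the FAS, gives rules for partial treatment dates, and then says "Other missing data will not be replaced". A patient without a Day 8 visit therefore drops out of every Day 8 secondary comparison.

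**Withdrawals.** SAP 4.3 and 6.2 allow an early withdrawal visit to be reassigned to the closest missing planned visit, Day 8 included. SAP 2.1 says the nearest non-missing visit, so membership of the Day 8 set is not consistently defined.

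**The concern.** Randomisation makes the two arms comparable as randomised. It does not make comparable the subsets who later choose, or are asked, to come to an extra visit. The stated trigger is perceived need, which plausibly tracks how the eye feels or looks after a week on the product. The products differ visibly and patients are not masked (Protocol 6.1), so a patient who knows the product may prompt the visit. Early withdrawals moved to Day 8 add a second group whose presence may depend on outcome.

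Nothing in either document limits Day 8 to description, accounts for the decision to attend, or warns the reader. SAP 5.4 says only that non-primary endpoints are of secondary importance and tested at 5% without adjustment. That concerns multiplicity, not selection. What is at stake is a set of Day 8 estimates and p-values, tabulated beside the scheduled visits, that could be read as randomised evidence on early effect.

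**Working it through.** **1. The plan's own figure.** The only sizing is for Day 35. With margin 2, SD 2.5, no true difference and one-sided 2.5%, 38 per arm gives 93.1% power (noncentral t), so the stated minimum of 90% holds. 76 / 0.85 = 89.4, which rounds up to the planned 90. SAP 5.1 reports 101 randomised. No figure is given for Day 8 attendance or precision.

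**2. Count of Day 8 tests (SAP 6.7.2).**

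| Endpoint | Test | Number |
|---|---|---|
| Oxford total, two eyes | ANCOVA | 2 |
| Van Bijsterveld, two eyes | ANCOVA | 2 |
| OSDI | ANCOVA | 1 |
| Schirmer, two eyes | ANCOVA | 2 |
| Mean TBUT, two eyes | ANCOVA | 2 |
| Symptom total score | ANCOVA | 1 |
| Hyperaemia, two eyes | CMH | 2 |
| Seven symptoms | CMH | 7 |

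That is 10 + 9 = 19 per set, and 2 × 19 = 38 over PP and FAS. The OSDI-class CMH test is not counted, since it is limited to Day 35 and Day 84. The instillation score (SAP 6.8.1) is not counted either, since the visit of its test is not stated.

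**3. When selection distorts the comparison.** Assume no true difference, SD 2.5 (the plan's Day 35 value, used here for Day 8), and attendance linked to the Day 8 outcome by a latent correlation r. If a proportion p attends, the attenders' mean is shifted by 2.5 × r × h(p), where h(p) = φ(z)/p and z is the upper-p normal quantile. Values: h(0.2) = 1.400, h(0.3) = 1.159, h(0.4) = 0.966, h(0.5) = 0.798, h(0.6) = 0.644. The spurious difference is the shift in one arm minus the shift in the other. False-positive rates come from a simulation with 50 per arm, a two-sided 5% t-test without baseline adjustment, and 8,000 runs.

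| Assumed attendance | r | Spurious difference (points) | Simulated difference | Simulated false-positive rate |
|---|---|---|---|---|
| 40% and 40% | 0.5 in both | 0 | 0.0 | 4.6% |
| 30% and 50% | 0 in both | 0 | 0.0 | 5.1% |
| 30% and 50% | 0.3 in both | 2.5 × 0.3 × (1.159 − 0.798) = 0.27 | 0.27 | 6.3% |
| 30% and 50% | 0.5 in both | 2.5 × 0.5 × (1.159 − 0.798) = 0.45 | 0.45 | 9.0% |
| 20% and 60% | 0.5 in both | 2.5 × 0.5 × (1.400 − 0.644) = 0.95 | 0.93 | 18.8% |
| 40% and 40% | 0.5 in one arm only | 2.5 × 0.5 × 0.966 = 1.21 | 1.20 | 33.8% |

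Under no true difference, the first two rows show no distortion. It appears when attendance is related to outcome and either the rates or the mechanism differ between arms. Every attendance rate and correlation here is an assumption.

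**4. Precision.** Even without bias, fewer patients are compared. With m attenders per arm, the half-width of the 95% CI is t(0.975; 2m − 2) × 2.5 × √(2/m). Taking 38 per arm as full attendance:

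| Attendance | m | Half-width (points) |
|---|---|---|
| 100% | 38 | 1.14 |
| 50% | 19 | 1.65 |
| 30% | 11.4 | 2.18 |
| 20% | 7.6 | 2.77 |

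**5. Reach beyond the secondary endpoints.** The primary analysis is an ANCOVA of observed Day 35 values in PP (SAP 6.7.1) and uses no Day 8 value. Day 8 can enter the FAS confirmation through LOCF. It also appears to enter the MMRM: the ESTIMATE statement of model (4) has three visit positions per arm with Day 35 second. SAP 5.2 assumes missing at random for that model.

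**The case against.** The strongest reply is that a risk of bias is not bias. The documents say only that someone thinks the visit necessary. They give no evidence that attendance depends on outcome or differs by arm, and the first two simulated cases show no distortion. The investigator can also call the visit, the examining investigator is masked, and patients are told not to disclose their product (Protocol 6.1), so attendance is not purely the patient's choice. All of this stands, and it rules out saying that the Day 8 estimates are biased.

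A reader might also infer that an early effect would be largely hidden. If only patients more than 1 SD above the comparator mean attended, a true difference of 0.5 SD would appear as 1.641 − 1.525 = 0.116 SD. That is an extreme assumption: neither the cut-off nor the effect is in the documents, and the same rule gives zero distortion when there is no true difference. It should not be used as an estimate of harm.

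It can further be said that the tests are secondary, that the protocol lists them (6.3.2 and 7.3.3), and that SAP Table 1.5 already shows by arm whether the Day 8 visit took place. These points lower the priority. They do not answer the concern: a yes/no count lets the reader see unequal attendance but not whether attenders are comparable, and nothing tells the reader to treat the p-values differently.

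**Conclusion.** The point holds as a risk. Followed as written, the plan produces 19 Day 8 comparisons per analysis set on a subset formed after randomisation, at a visit triggered by perceived need, with no imputation and possibly with reassigned withdrawals. Their p-values lack the protection of randomisation. The size and direction of any bias are unknown; the assumed cases run from none to about 1.2 Oxford points and a false-positive rate of about 34%. The figures use the plan's Day 35 SD at Day 8 and an unadjusted t-test, so they illustrate and do not predict.

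A reader might infer that the non-inferiority conclusion is compromised. The documents do not support that: the deciding analysis is the observed-case Day 35 ANCOVA in PP, and no Day 8 value enters it. This is a worthwhile and cheap improvement to the secondary analyses, not a flaw in the primary one.

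**What to change.** Before unblinding, add an entry to SAP 4.3 stating that Day 8 results are descriptive: number attending, mean and SD by arm (counts and percentages for the categorical endpoints), shown next to the planned table of visits performed. Restrict the secondary ANCOVA and CMH tests in SAP 6.7.2 to Day 35 and Day 84. If the sponsor prefers to keep the protocol's Day 8 comparisons, label their p-values explicitly as non-inferential and say why. Report a reason for attending only if one was collected; neither document shows that it was. Use one rule for reassigning withdrawal visits in SAP 2.1, 4.3 and 6.2, and show how many Day 8 records come from it.

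Optionally, add one MMRM run on Day 35 and Day 84 only, as a check that the sensitivity analysis does not lean on the optional visit.

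Cost: no new data. Comparisons listed in Protocol 7.3.3 lose their formal Day 8 p-values, which is a recorded departure from the protocol. The Day 8 parts of ten pairs of ANCOVA tables (5.7, 5.10, 5.13, 5.16, 5.22, 5.25, 5.27, 5.30, 5.33, 5.38) change, as do the Day 8 comparisons for hyperaemia and symptoms.
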